**Abbreviation Note:**

IUD = intrauterine device (can be either copper or hormonal (levonorgestrel or LNG);

IUS = intrauterine system (refers to the LNG-IUS or Mirena IUD);

In this protocol, we may refer to the LND-IUS or LNG-IUD (synonyms)

**BACKGROUND & SIGNIFICANCE:**

Among the most frequently used methods of contraception are daily-dosing regimens such as oral contraceptive pills, or coital-dependant methods such as condoms. These methods have high typical use failure rates (> 8%) contributing to the unintended pregnancy rates in the United States that approach 50% each year. Unintended pregnancy has serious economic and social consequences for both individuals and society as a whole. Emergency contraception (EC) has been shown to be effective in preventing pregnancy when used within 120 hours of unprotected or under-protected intercourse. Disappointingly, EC has not made a dramatic impact on abortion rates. The most common regimen used today is a progestin-only (levonorgestrel) oral regimen which has been shown to reduce pregnancy risk by 60-94%. The copper T-380 intrauterine device (IUD) has been shown to have even greater efficacy reducing the risk of pregnancy by 99%. This method is not as commonly used, likely because of high up-front cost or associated side-effects. A recent observational feasibility study provided promising results; when offered a choice of the oral levonorgestrel (LNG) regimen or copper T-380 IUD, the ratio of oral LNG to IUD users was 1.5 to 1. This study demonstrated that when cost and access barriers are removed, women are willing to use the intrauterine device for EC. The copper intrauterine device has the added benefit of continued highly effective contraception for up to ten years which has the potential to impact unintended pregnancy rates.

There is a second, more popular intrauterine contraceptive method available in the U.S, the levonorgestrel intrauterine system (LNG-IUS), which has not yet been evaluated as an emergency contraceptive method. The LNG-IUS is more appealing to women as it offers many noncontraceptive benefits with many users reporting lighter and less painful menses. There are currently no data available evaluating the LNG-IUS as a method of emergency contraception. However, several of the mechanisms by which the LNG-IUD is thought to work suggest that suggest it may be effective in the post-coital (EC) setting. Potential mechanisms include both pre- and post-fertilization effects. Pre-fertilization effects include disruption of sperm motility and viability, alteration in the speed of ovum transport, and direct damage to the ovum. Immediate endometrial changes initiated by both the LNG and copper-IUD likely inhibit sperm migration in a spermicidal fashion. Additionally, the decidualization process initiated by the LNG-IUD may also inhibit sperm survival. Postfertilization mechanisms include slowing of embryo transport, destruction of the embryo during transit, and prevention of implantation. Both IUDs have been shown to produce cytokines and integrins within the endometrial lining that would likely prevent implantation. Lastly, an inflammatory response of the endometrial lining most likely contributes to the prevention of implantation in LNG-IUD users.

The proposed research is designed to evaluate the pregnancy rates in women using the LNG-IUS for EC. We expect to show that the LNG-IUS can be used as an effective method of emergency contraception and has higher efficacy rates than oral EC. Confirming effectiveness of the LNG-IUS in this setting will expand access and uptake. *Increasing the use of intrauterine contraception as a method of emergency contraception and providing long-term reversible contraception, has the potential to significantly reduce unintended pregnancy and abortion rates.* In 2009, the Institute of Medicine declared expanding access to long-acting reversible

contraceptive (LARC) methods one of the top priorities of comparative effectiveness research, and this study will help reach that goal.

## INNOVATION:

There are currently no data addressing the use or effectiveness of the LNG-IUS as a method of emergency contraception. This proposal will provide essential information to both patients and clinicians in this field. Specifically, the LIFE study (levonorgestrel IUS For Emergency contraception) will answer the following questions:

- 1) Is the LNG-IUS an effective method of emergency contraception?
- 2) Is the LNG-IUS more effective than the oral levonorgestrel regimen?
- 3) Are women receiving LNG-IUS more likely to be using a LARC method at 6 months?
- 4) Are women receiving the LNG-IUS as emergency contraception still using and satisfied with their method at 6 months and at 12 months?

Current practices in the United States provide women 4 choices of EC. A modified regimen of combined oral contraceptives (Yuzpe method) has been shown to be the least effective and associated with the most side-effects. There are two additional oral regimens, the levonorgestrel and ulipristal acetate regimens which are effective for a single act of unprotected intercourse. The most commonly-used method is the oral levonorgestrel regimen which is largely available over the counter. Ulipristal acetate is the newest regimen, approved by the FDA in August 2010, requires a physician prescription, and is more expensive than the levonorgestrel option. The most effective, least used and most expensive method of EC is the Cu-T380. This method, unlike the previous methods, provides continued highly effective long-term contraception. The levonorgestrel-IUS is the only other intrauterine device available in the U.S. The LNG-IUS is currently used only for standard contraception, not emergency contraception. In this setting it has been shown to be highly effective, convenient, forgettable, cost-effective, and extremely well-liked by users. *This research is innovative, because we will be evaluating a new method of emergency contraception and expanding access to include a well-liked, long-term, and extremely effective method of contraception that has the potential to reduce unintended pregnancy and abortion rates.* The American College of Obstetricians and Gynecologists Committee on Gynecologic Practice Opinion, published in 2009 suggested that the high rates of unintended pregnancy may be a direct consequence of low use of long acting reversible contraceptives.

## APPROACH

General: The purpose of this proposal is to recruit 532 women experiencing an act of under-protected intercourse, defined as a breech or incorrect use of a contraceptive method or no method use at all, who do not desire pregnancy at this time.

Participants will be randomized to ulipristal acetate (the most effective oral EC available) or to the study therapy, levonorgestrel intrauterine system (LNG-IUS). The primary outcome of this study is pregnancy occurring despite treatment. We will address the following specific aims:

**Primary Aim:** Our *primary aim* is to evaluate the effectiveness of the LNG-IUS as a method of emergency contraception (EC) by comparing observed pregnancy rates in those receiving oral ulipristal acetate (UPA) and LNG-IUS. The *objective* of this aim is to provide evidence that will expand access to this highly effective

method of long term contraception. We will perform a randomized controlled trial comparing pregnancy rates in women receiving the LNG-IUS to those receiving the oral EC.

*Hypothesis:* The LNG-IUS will be more effective than the oral UPA as a method of EC and through 6 months after enrollment.

The *rational* for this aim is that successful completion of this project will provide important evidence for an alternative method of emergency contraception. It is our *expectation* that the knowledge gained from completion of this project will reduce barriers to intrauterine contraception, thereby increasing the number of women using the method, and subsequently impacting unintended pregnancy and abortion rates.

**Secondary Aim 1:** Our secondary aim is to evaluate long-acting reversible contraceptive (LARC) use at 6 and 12 months following initial treatment. The *objective* of this aim is to demonstrate that offering LARC as EC can increase the number of women using the most effective methods of contraception.

*Hypothesis:* When compared to women who receive the oral UPA, women who receive intrauterine contraception as a form of EC have higher rates of LARC use at 6 and 12 months.

It is our *expectation* that the anticipated difference in LARC use at 6 and 12 months between the two groups will provide supportive evidence for the importance of reducing barriers to intrauterine contraception by offering it as a method of EC.

**Secondary Aim 2:** One secondary aim of this project is to quantify the contraceptive continuation and satisfaction rates of the participants randomized to LNG-IUS. The objective of this aim is to demonstrate that if women have access to the LNG-IUS in this time period, most will continue use for at least 12 months and will have high levels of satisfaction. *Hypothesis:* Greater than 70% of women receiving the LNG-IUS as EC will have continued use and satisfaction.

It is our *expectation* that the information gained from completion of this aim will contribute to the growing body of literature describing continuation and satisfaction rates among different groups of LARC users.

### **Research Design and Methodology:**

Research design and general methodological approach: We will perform a randomized control trial comparing oral UPA to LNG-IUS for emergency contraception. We will prospectively enroll 532 women experiencing an act of under-protected intercourse within the previous 5 days (120 hours). Participants with a negative pregnancy test, and who meet all inclusion criteria, will be randomized to either an immediate LNG-IUS insertion or oral UPA EC regimen (30mg ulipristal acetate) in a 3:1 ratio. Participants will be provided with a pregnancy test to perform at home and will be called to report the results of the urine pregnancy test 5-6 weeks after insertion. Participants receiving the LNG-IUS will also be return for a brief visit to check LNG-IUS strings. Participants will be contacted via telephone at 6 and 12months post enrollment to complete a follow-up survey. The primary outcome of this study is observed pregnancy rates at 5 weeks and 6 months after enrollment.

Criteria for selection of subjects: Potential participants for this study will be identified in as follows: 1) Women enrolled in the Contraceptive CHOICE Project (CHOICE) who are not currently using a long acting reversible contraceptive (LARC) method and have experienced an act of under-protected intercourse in the previous 5

days; 2) Women presenting, either in person or via telephone contact, to the Barnes Jewish Hospital Women's Health resident OB/GYN clinic who have experienced an act of under-protected intercourse in the previous 5 days; 3) Women identified from an advertising campaign; and

Enrollment: All potential participants receive informed consent and will be directed to make an appointment for consent, randomization, and allocation of method.

Inclusion Criteria:

- Women age 14-45
- Under-protected intercourse within the last five days (120 hours)
- Willingness to accept either IUS intervention or oral EC
- Ability and willingness to follow-up via telephone for results of a urine pregnancy test (UPT)
- Ability and willingness to be contacted by phone for 6 and 12 month follow-up

Exclusion Criteria:

- Positive pregnancy test
- Non-English speaking
- Contraindication to intrauterine contraception or oral UPA
  - Active cervicitis, PID, or recent post-abortal or postpartum infection
  - Undiagnosed abnormal uterine bleeding
  - Known or suspected cervical or endometrial neoplasia
  - Known or suspected breast cancer or other progestin-sensitive cancer
  - Uterine anomalies that preclude IUD insertion
- Inability or unwillingness to comply with follow-up

Randomization: A permuted block randomization scheme will be created using the nQuery software (Statistical Solutions, Saugus, MA) using a computerized random number generator. Block sizes will vary, and will be balanced within each recruitment site. Assignment will be concealed in sealed, opaque envelopes. Participants will be randomly assigned to LNG-IUS or oral UPA with a 3:1 ratio.

Description of drugs and devices:

The U.S. Food and Drug Administration (FDA) approved the LNG-IUS in 2000 as a 5-year method of reversible contraception. The device contains 52 mg of levonorgestrel which is slowly released at a rate of 20 mcg/day into the uterus. The device is safe, effective and easy to use in almost all populations. The standard contraceptive mechanism of action is through cervical mucus thickening and endometrial lining suppression. The device has not yet been evaluated as a method of emergency contraception. However, the WashU study team submitted an IND application to the FDA, and obtained an IND to study the device as a method of EC. A clinician trained in IUD insertions will insert the LNG-IUS.

The FDA first approved oral levonorgestrel with a dedicated indication for emergency contraception in 1998. There are currently two acceptable dosing protocols, single-dose, and two-dose, both of which contain a total of 1.5 mg of levonorgestrel. There are several proposed mechanisms by which this regimen reduces pregnancy: inhibited or delayed ovulation, interference with sperm transport and penetration, and

endometrial changes decreasing receptivity. It has been shown to have no effect on an already established pregnancy and is not a form of medical abortion.

The FDA approved Ulipristal acetate in August 2011(ulipristal acetate) is a synthetic progesterone agonist/antagonist. When taken immediately before ovulation is to occur, Ella postpones follicular rupture. The likely primary mechanism of action of ulipristal acetate for emergency contraception is therefore inhibition or delay of ovulation; however, alterations to the endometrium that may affect implantation may also contribute to efficacy.

Ulipristal acetate (UPA) is specifically indicated as an emergency contraceptive for prevention of pregnancy following unprotected intercourse or a known or suspected contraceptive failure. UPA is supplied as a tablet for oral administration. The recommended dose is one 30 mg tablet taken orally as soon as possible, within 120 hours (5 days) after unprotected intercourse or a known or suspected contraceptive failure.

Complete descriptions of both LNG-IUS (Mirena) and UPA (Ella) are provided in the Package Inserts. Copies of each package insert are provided in the Appendices.

#### Evaluation/ Follow-Up:

At enrollment all women will undergo a highly sensitive urine pregnancy test as well as self-collected vaginal swab for sexually transmitted disease (STI) testing for *Neisseria gonorrhoeae* and *Chlamydia trachomatis*. Randomization and allocation of emergency contraceptive method will occur immediately following consent. A positive test for an STI will not exclude the patient from participation. All positive *N. gonorrhoeae* or *C. trachomatis* tests will be treated with standard CDC-approved treatment. Partner treatment will also be offered. Women randomly assigned to the LNG-IUS group will be asked to return at 5-6 weeks for a string check. All participants will be provided a urine pregnancy test at enrollment and will be called at 5 weeks post enrollment to obtain results. Participants will then be contacted to complete a follow-up surveys at 6 and 12 months following enrollment.

Measures: Urine pregnancy test results will be documented at 5-6 weeks following method allocation. Negative urine pregnancy tests will be validated by a normal menses after enrollment. Participants testing positive at home will be asked to come into the study site for pregnancy test validation and options counseling. We have studied over 9,000 women attempting to avoid unintended pregnancy in the Contraceptive CHOICE Project. Participants were able and willing to report home pregnancy testing results and/or return for a visit for a sensitive pregnancy test. Any woman who suspects pregnancy, is late for her routine menstrual cycle, or who reports a positive home test will be asked to return to our clinic for pregnancy test validation and options counseling (offered option of continuing the pregnancy or pregnancy termination). *We are using the CONSULT urine pregnancy test which is sensitive to a hcg level of 20mIU/mL with a specificity of >99% (Appendix A).*

Women enrolled in an EC study are clearly motivated to avoid an unintended pregnancy. A negative home pregnancy test and regular menses reliably excludes an on-going pregnancy. Self-report of a negative test and menses will not be validated, as they are acceptable measures to reliably exclude pregnancy. Pregnancy

testing in this protocol has been used for the CHOICE project, with two peer-reviewed publications accepted to the New England Journal of Medicine (Winner B. et al. 2012 & Secura G. et al. 2014)

At the follow-up phone surveys, individual level information will be updated with new medical data including any new medical diagnosis, interval pregnancies since enrollment, and interval diagnosis of STIs. We will also assess fertility desires, recent and current contraceptive use, and recurrent emergency contraception utilization.

**Primary Outcome:** The **primary outcome** of this study is unintended pregnancy following emergency contraception at both 5 weeks and 6 months post-enrollment.

**Secondary Outcomes:** 1. Long acting reversible contraception (LARC) use at 6 and 12 months following method allocation will be evaluated. 2. Continuation and satisfaction among participants in the LNG-IUS arm.

**Potential Confounders:** There are a number of variables that make act as potential confounders. These variables will be tested for their association with the primary outcome and treatment assignment. Age is strongly associated with fertility. Other potential confounders include: race/ethnicity, socioeconomic status (measured by income or education level), history of sexually transmitted infection or pelvic inflammatory disease, previous or current contraceptive method. Given random assignment, we expect two arms will be balanced in terms of known and unknown confounding variables. However, if any imbalance is noted, we will control for possible confounders in our multivariable statistical analysis.

**Data Management:** Study staff located within the Division of Clinical Research will be responsible for data collection, entry, and management. Off-site staff will enroll participants remotely using the RedCap secure website. All telephone follow up surveys will be conducted by study staff of Washington University in St. Louis, School of Medicine. Data from telephone interviews will be entered using a secure web portal and stored on secure Washington University in St Louis Department of Obstetrics and Gynecology servers. All participants will be assigned a study identification number. This study I.D. will be used on all data forms and for all computer entries. Data entry will be completed using a custom software package (Illume™; DatStat Inc., Seattle, WA). The data manager will be responsible for data processing, validity checks, and communication with the team on data issues.

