**ADVERSE REACTIONS:** There are few side effects of UPA and LNG-IUS. These are listed in the protocol and informed consent form. Most side effects resolve spontaneously. Anticipated events means reactions to treatment previously observed that may require medical intervention but are not serious in nature.

All adverse events that occur will be recorded in the Source Documents. Adverse events should be captured in the medical history.

Adverse Events occurring will be captured and followed until the condition resolves, stabilizes, or is otherwise explained, or the subject is lost to follow-up. Subjects will be instructed that they may contact one of the Principal Investigator at any time throughout the course of the study.

The Investigator will review each event and assess its relationship to method of EC (not related, unlikely, possible, probable, and highly probable). The following definitions will be used for rating relationship to the treatments or investigational device:

- Not related – The event is clearly related to other factors such as the subject's clinical state, therapeutic interventions, or concomitant medications administered to the subject.
- Unlikely – The event was most likely produced by other factors such as the subject's clinical state, therapeutic interventions, or a concomitant medication administered to the subject; and does not follow a known response pattern to the investigational device.
- Possible – The event follows a reasonable temporal sequence from the time of investigational device administration; and/or follows a known response pattern to the study treatments; but could have been produced by other factors such as the subject's clinical state, therapeutic interventions, or concomitant medications administered to the subject.
- Probable – The event follows a reasonable temporal sequence from the time of investigational device administration; and follows a known response pattern to the investigational device; and cannot be reasonably explained by other factors such as the subject's clinical state, therapeutic interventions, or concomitant medications administered to the subject.

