## Risks and Benefits

The interventions compared in this trial are oral UPA versus LNG-IUS. No serious or life-threatening adverse events are expected. Nonetheless, the following measures will be taken to monitor and investigate adverse events. Immediate EC failures should be uncommon. If more than one pregnancy occurs in the LNG-IUS arm, an urgent DSMB meeting will be convened to discuss the preliminary outcomes. These immediate failures must be put into context of the number of long-term (6 and 12-month) failures to determine if the trial will continue.

According to the Prescribing Information, the most common adverse reactions ( $\geq 5\%$ ) to UPA are headache (18%), abdominal pain (12%), nausea (12%), dysmenorrhea (9%), fatigue (6%), and dizziness (5%). The most common adverse reactions to the LNG-IUS reported in clinical trials ( $> 10\%$  users) are uterine/vaginal bleeding alterations (51.9%), amenorrhea (23.9%), intermenstrual bleeding and spotting (23.4%), abdominal /pelvic pain (12.8%) and ovarian cysts (12%). With any IUD insertion, there are risks of infection (<1%) and uterine perforation (approximately 0.1%).

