## **Retention Plan**

As in past contraceptive studies, we will provide incentives to assist with transport and childcare. We plan to closely monitor follow-up rates as well. When participants enroll, we will collect contact information to include the participant's address; home, cell and work phone numbers; email address; and contact information for two alternate contacts as well.

Participants are called 5-weeks post enrollment, six-months post enrollment and 12-months post enrollment for short follow up surveys. They are provided a gift card with each completed survey. Participants are able to schedule calls or complete them at the time of contact. At each survey they are reminded that we will be calling them back in a specific time frame.

Participants are contacted at their preferred contact method which is usually a cell phone. If, after 2 attempted calls they are not reached or do not call back, a call is made to alternate contact numbers for the participant; email contact is then attempted, if the participant has still not responded alternate contacts are called.

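### Adverse event detection may differ by arm: only LNG-IUS participants have a scheduled return visit, and no common adverse event checklist is described

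*Combined protocol and SAP*

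**What the plan says.** **Contacts after treatment.** The Retention Plan sets the same telephone schedule for everyone: "Participants are called 5-weeks post enrollment, six-months post enrollment and 12-months post enrollment for short follow up surveys". The LNG-IUS arm has one contact more. Research Design and Methodology says "Participants receiving the LNG-IUS will also be return for a brief visit to check LNG-IUS strings", and Evaluation/Follow-Up gives the timing: "Women randomly assigned to the LNG-IUS group will be asked to return at 5-6 weeks for a string check". No return visit is scheduled for the UPA arm.

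**What the calls collect.** Under Evaluation/Follow-Up, "individual level information will be updated with new medical data including any new medical diagnosis, interval pregnancies since enrollment, and interval diagnosis of STIs". The same paragraph adds fertility desires, contraceptive use and repeat use of emergency contraception.

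**How adverse events are recorded.** Adverse Reactions states "All adverse events that occur will be recorded in the Source Documents" and then "Adverse events should be captured in the medical history". Each event is rated for relatedness and severity and followed to an outcome.

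**Other routes, open to both arms.** Participants may contact an investigator at any time (Adverse Reactions). Women who suspect pregnancy, have late menses or test positive at home are asked back to clinic (Evaluation/Follow-Up).

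**Analysis.** Adverse events are not among the primary or secondary outcomes, and neither statistical section plans a comparison of them between arms.

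**The concern.** Recorded adverse event rates reflect both how often events happen and how hard the trial looks for them. Here one arm has an extra face-to-face contact, and the shared route as described suits diagnoses better than symptoms. All six common UPA reactions listed in Risks and Benefits, from headache (18%) to dizziness (5%), are symptoms that a woman might never take to a doctor. The first scheduled contact after the tablet is a call about 5 weeks later. A brief reaction on the day of dosing could easily go unmentioned when the question is about new diagnoses.

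The safety data matter even without a formal test. The LNG-IUS is being studied under an IND for a new use, results may be reported to the FDA, side effects can lead to removal of a participant, and the study can be stopped for safety. If the LNG-IUS arm is observed more closely, its safety profile may look worse beside UPA than it is. Symptoms never recorded cannot be recovered at the analysis stage.

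**Working it through.** The plan gives no adverse event detection rate and no expected difference between arms, so there is no figure of its own to reproduce. The check has two parts.

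**1. Routes of detection by arm**

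| Route | LNG-IUS | UPA |
|---|---|---|
| Calls at 5 weeks, 6 and 12 months | yes | yes |
| Spontaneous contact with an investigator | yes | yes |
| Unscheduled visit for suspected pregnancy, late menses or positive test | yes | yes |
| Clinician pelvic exam and insertion at enrollment (Study Flow) | yes | not listed |
| Scheduled return visit at 5-6 weeks | yes | no |

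The third route is open to both arms but may not be used equally. Risks and Benefits gives amenorrhea in 23.9% of LNG-IUS users, which could bring more late-menses visits in that arm. No listed route is open to the UPA arm alone, so any imbalance probably runs towards more recorded events with the LNG-IUS.

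**2. Illustration of size, with equal true rates**

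All three inputs are assumptions:
- *s*: share of events found by the routes common to both arms
- *v*: share of the events so missed that the string check finds
- *r*: attendance at the string check

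Detection in the UPA arm is *s*. Detection in the LNG-IUS arm is 1 − (1 − *s*)(1 − *v r*). The ratio of recorded rates, LNG-IUS to UPA, is therefore 1 + *v r* (1 − *s*)/*s*.

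| *s* | *v* | *r* | LNG-IUS detection | Ratio | Recorded at a true rate of 10%, UPA v LNG-IUS |
|---|---|---|---|---|---|
| any | 0 | any | *s* | 1.00 | equal |
| 0.9 | 0.2 | 0.8 | 1 − 0.1 × 0.84 = 0.916 | 1.02 | 9.0% v 9.2% |
| 0.7 | 0.5 | 0.8 | 1 − 0.3 × 0.60 = 0.82 | 1.17 | 7.0% v 8.2% |
| 0.5 | 0.5 | 0.8 | 1 − 0.5 × 0.60 = 0.70 | 1.40 | 5.0% v 7.0% |
| 0.4 | 0.5 | 0.8 | 1 − 0.6 × 0.60 = 0.64 | 1.60 | 4.0% v 6.4% |
| 0.2 | 0.5 | 0.8 | 1 − 0.8 × 0.60 = 0.52 | 2.60 | 2.0% v 5.2% |

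Over *s* = 0.5 to 0.9, *v* = 0 to 0.5 and *r* = 0.5 to 0.8, the ratio lies between 1.00 and 1.40. The last two rows show what it takes to go higher: the shared routes must miss 60% to 80% of events while the visit finds half of what they missed.

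For scale, suppose someone did test one event type between arms. The planned 133 and 399, less the 20% loss allowed for, leave about 106 and 318. In the *s* = 0.5 row at a true rate of 10%:
- the null standard error is √(0.065 × 0.935 × (1/106 + 1/318)) = 0.0277
- the standard error under the two recorded rates is √(0.05 × 0.95/106 + 0.07 × 0.93/318) = 0.0255
- the chance of a false significant LNG-IUS excess is Φ((0.020 − 1.96 × 0.0277)/0.0255) ≈ 9%, against a nominal 2.5% in that tail

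At a true rate of 20% the same row gives about 17%.

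**The case against.** The other side has several good points.

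- **The visit is described only as a string check.** A reader might infer that adverse events are solicited in person in one arm and merely volunteered in the other. The documents do not say so: neither description of the visit mentions an adverse event enquiry, and the only active enquiry described is the telephone update, which both arms receive. This stands, and it is why the effect may be zero.
- **The survey instruments are not shown.** The call steps in Study Flow give logistics and one line to administer the survey. They do not mention the pregnancy test result either, which is the purpose of the 5-week call. The absence of an adverse event question there proves little, and the description of the telephone update is not worded as a complete list. This stands too. If a common symptom question exists, the protocol should state it.
- **Event-level handling is required.** A reader might infer that events filed in the medical history cannot be told from pre-existing conditions. That goes too far, since source documentation, relatedness, severity and outcome are all required for each event.
- **The consequence is limited.** No between-arm test is planned. Serious events are defined by outcomes such as hospitalization, which depend little on a string check. The one stated trigger for an urgent DSMB meeting is pregnancies in the LNG-IUS arm, not an adverse event rate.
- **The string check is legitimate device follow-up** with no tablet equivalent, and a table built only on calls could hide device problems. This is met by also reporting all events by source.

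What remains is unequal scheduled contact with no described common instrument to offset it.

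**Conclusion.** The point holds as a risk of unequal ascertainment, probably towards more recorded events in the LNG-IUS arm. It is not a demonstrated bias. A reader might infer that rates will differ, that UPA reactions are certainly under-recorded, or that the LNG-IUS will show an excess of twofold or more. None of these follows from the documents. The ratio of recorded rates is 1.0 if the string check finds nothing extra and about 1.4 at the top of the main assumed range. It reaches 1.6 to 2.6 only if shared detection is put at 40% to 20%. Every one of these figures rests on assumed detection and attendance.

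The effect falls on descriptive safety tables and safety review. The pregnancy outcome and its sample size are not affected by this point. It is still worth acting on, because the remedy is cheap and must be in place before the events occur.

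**What to change.** 1. Add one closed adverse event checklist to the 5-week, 6-month and 12-month calls, in the same words and order in both arms. Cover the reactions that Risks and Benefits names for either product, together with the insertion risks given there. If the surveys already contain such questions, state this in the protocol.
2. Enter each event on an adverse event form with its onset date and source of detection (call, string check, unscheduled visit or spontaneous report), rather than only in the medical history.
3. Say in the analysis section that any by-arm adverse event table uses call-elicited events. Alongside it, report all events by source, including those found only at the string check, so that no device event is lost.

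The cost is survey and form wording and a minute or two on calls planned to take less than 10 minutes, with no extra visit or staff. Some recall error at 5 weeks will remain. So will any difference in reporting that arises because women know which treatment they received; a common checklist reduces unequal questioning but cannot remove that.
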